### **PK Analysis Plan**

PK parameters will be estimated by non-compartmental analysis using WinNonlin software. The plasma concentrations-time profiles of each study drug will be presented in figure form by participant and cohort. The appropriate non-compartmental pharmacokinetic parameters will be computed, including  $AUC_{0-24}$ ,  $AUC_{ss}$ ,  $C_{max}$ ,  $CL$ ,  $V_{ss}$ , and  $t_{1/2}$ . PK parameters will be summarized by age cohort. The influence of covariates on PK parameters will be explored. If not enough samples are obtained per subject to allow for noncompartmental analysis, a population PK analysis approach will be used.

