2. GA/PNA
  - i. Rifampin: <121 days PNA
  - ii. Ticarcillin-clavulanate: <91 days PNA AND <30 weeks GA
  - iii. Clindamycin: <121 days PNA AND <30 weeks GA
3. Sufficient intravascular access
4. Suspected systemic infection

OR

Receiving 1 of the study drugs per local standard of care

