#### **7.1.2 Rifampin, ticarcillin-clavulanate, and clindamycin local standard of care dosing**

If the site Principal Investigator deems it appropriate for the infant to receive the local standard of care dose, this SOC dose may be selected and administered as the study dose throughout the on-study dosing period.

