#### **8.1.4 Interim Safety Analysis**

**Rifampin:** The study team will evaluate safety after 3 participants are enrolled in each cohort and receive the protocol dose. The safety review will be performed within 1 week after all data on the third participant in each cohort are entered and there are no pending queries. Enrollment in the cohort will be halted if there are any safety concerns.

**Clindamycin:** The study team will evaluate safety after 3 participants ≤26 weeks gestation are enrolled in cohort 1. The safety review will be performed within 1 week after all data on the third participant ≤26 weeks gestation in cohort 1 are entered and there are no pending queries. Enrollment for infants ≤26 weeks gestation in cohort 1 will be halted if there are any safety concerns. During the safety review, enrollment in this cohort will continue except for infants ≤26 weeks gestational age at birth.

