#### Population for Analysis

All participants who receive at least 1 dose of study drug will be evaluable for safety profile analysis. All participants that provide at least 1 PK sample will be included in the PK analysis.

Pharmacokinetic data from premature infants collected in the Pharmacokinetics of Understudied Drugs Administered to Children per Standard of Care (POPS) trial will be combined and co-modeled with data from the Staph Trio trial. Inclusion of POPS data will increase the sample size across all cohorts, allow for model evaluation/validation using data from an independent trial and likely result in more precise estimation of model parameters.

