#### **Interim PK analysis**

**Rifampin:** An interim PK analysis will be performed after enrollment of 3 participants in each cohort for rifampin. If the interim analysis suggests the PK data are sufficient to describe rifampin disposition in this patient population, enrollment will stop after 8 participants are enrolled in each cohort. If additional participants are required, the interim PK data will be used to determine the number of additional participants.

**Clindamycin:** An interim PK analysis will be performed after enrollment of 3 participants in cohort 1 for participants  $\leq 26$  weeks gestational age. If the interim analysis suggests the PK data are sufficient to describe clindamycin disposition in this patient population, enrollment will stop after 8 participants are enrolled in each cohort. If additional participants are required, the interim PK data will be used to determine the number of additional participants.

For both analyses, if the PK analysis suggests that drug exposure is below the maximum tolerated exposure in adults, no dosing modifications will be made.

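### Section 7.1.2 lets a local dose replace the cohort dose, but 10.3 summarizes AUC and Cmax by age cohort with no regimen split or dose normalization

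*Protocol*

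**What the plan says.** Section 3.1.1 names six primary outcomes: AUC0-24, AUCss, Cmax, CL, Vss and t1/2. Section 7.1.1 sets a dose and interval for each GA/PNA cohort. Section 7.1.2 then adds that, where the site investigator thinks the local standard-of-care dose appropriate, "this SOC dose may be selected and administered as the study dose throughout the on-study dosing period". It puts no bounds on that dose or its interval. Infants already on local treatment are an expected part of the population, since one entry route in 5.2 is "Receiving 1 of the study drugs per local standard of care".

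Section 10.2 states: "All participants that provide at least 1 PK sample will be included in the PK analysis". It also says that premature-infant data from a standard-of-care trial "will be combined and co-modeled with data from the Staph Trio trial". In 10.3 the parameters are estimated non-compartmentally, with population PK as the fallback if samples are too few, and "PK parameters will be summarized by age cohort". Covariates will be explored, but neither dose nor regimen is named.

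On the interim look, 10.3 says "An interim PK analysis will be performed after enrollment of 3 participants in each cohort for rifampin". For clindamycin the trigger is three infants of at most 26 weeks' gestation in cohort 1. For both drugs, "if the PK analysis suggests that drug exposure is below the maximum tolerated exposure in adults, no dosing modifications will be made". The rifampin safety review in 8.1.4 differs: it takes place "after 3 participants are enrolled in each cohort and receive the protocol dose". The clindamycin safety review carries no such condition.

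**The concern.** AUC and Cmax are functions of the dose given. If some infants in a cohort receive the cohort dose and others a local one, the cohort mean of AUC or Cmax belongs to neither regimen, and its standard deviation mixes dose differences with between-infant variability. Section 7.1.1 argues for the rifampin doses by the exposure they might achieve, so a reader will take the cohort summary as exposure at the cohort dose. With mixed dosing it is not that.

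The same gap reaches the interim look. Exposure there decides whether doses are modified, yet nothing requires that the infants examined received the dose in question.

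**Working it through.** **Inputs from the protocol.** Rifampin cohort doses are 10, 15, 15 and 20 mg/kg q24h (7.1.1). The cited infant study used 5–10 mg/kg/day (2.1, 7.1.1). The planning CV for CL is 40% (10.2). Clindamycin cohort 1 receives 10 mg/kg q12h (7.1.1). The cited clindamycin study used 20 mg/kg/day divided q6–8h, with a half-life of 8.7 h in infants under 28 days (2.1).

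**Assumptions.** The local rifampin dose is 10 mg/kg q24h, with 5 mg/kg as the low end. The share p of a cohort on the local dose is 25, 50 or 75%. PK is linear and CL is lognormal with CV 40%. The documents give neither local doses nor shares.

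**The plan's own precision figure.** 1.96 × CV / √32 gives 13.9, 17.3, 20.8 and 27.7% for CVs of 40, 50, 60 and 80%. These match the stated 14, 17, 21 and 28%. That table concerns CL and is not in dispute.

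**Mixed-dose AUC0-24.** With AUC0-24 = daily dose / CL and r = local dose / cohort dose:

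- mean relative to protocol dose = (1 − p) + p·r
- CV² = 1.16 × [(1 − p) + p·r²] / [(1 − p) + p·r]² − 1

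For cohort 4 with p = 0.5 and r = 10/20: mean = 0.5 + 0.25 = 0.75; CV² = 1.16 × 0.625 / 0.5625 − 1 = 0.289, so CV = 53.7%. A simulation of 2,000,000 infants gave mean ratio 0.750 and CV 53.7%, returning to 40.0% after division by dose.

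| Rifampin cohort | Local dose | Mean, % of protocol-dose value (p = 25/50/75%) | CV, % |
|---|---|---|---|
| 1 | 10 mg/kg | 100 / 100 / 100 | 40 / 40 / 40 |
| 2 and 3 | 10 mg/kg | 92 / 83 / 75 | 43 / 45 / 45 |
| 4 | 10 mg/kg | 88 / 75 / 63 | 48 / 54 / 55 |
| 4 | 5 mg/kg | 81 / 63 / 44 | 59 / 76 / 89 |

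Linearity is not established in the documents. If AUC varies as dose^b, the 75% for half of cohort 4 becomes 79% at b = 0.8 and 72% at b = 1.2.

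**Interim look, rifampin.** If k of three infants are on 10 mg/kg, mean exposure is [(3 − k) + k·r]/3 of the protocol-dose value. For k = 1, 2, 3 this is 83, 67, 50% in cohort 4; 89, 78, 67% in cohorts 2 and 3; and 100% throughout in cohort 1. If the three are the protocol-dose infants of the safety review, there is no shift.

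**Interim look, clindamycin cohort 1.** The cited 20 mg/kg/day equals the cohort's daily dose (10 × 2), so AUC0-24 does not shift. Steady-state Cmax does. Assuming one compartment and the same 30-minute infusion, Cmax is proportional to dose / (1 − exp(−kτ)), with k = ln 2 / 8.7 h:

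- 5 mg/kg q6h against 10 mg/kg q12h: ratio 0.81
- 6.67 mg/kg q8h against 10 mg/kg q12h: ratio 0.87

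Per mg/kg these become 1.62 and 1.31, so dividing Cmax by dose over-corrects when the interval differs. Over half-lives of 3.6 to 20 h (upper end assumed) the ratios run 0.66–0.91 and 0.76–0.94.

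**The case against.** The best reply is that splitting a table by regimen is ordinary SAP detail. Section 10.3 does not say that age cohort is the only grouping, doses are recorded, covariates will be explored, and the stated objective is to describe the PK, not to test exposure at a given dose. The planned co-modeling uses actual doses and could predict exposure under any regimen. The interim wording also does not say that exposure is judged by a raw mean of three infants.

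Much of this stands as a limit on the point. It does not remove it. The protocol itself declares AUC and Cmax primary and fixes their grouping. That grouping, applied as written, pools doses that 7.1.2 allows to differ. Unspecified covariate exploration and co-modeling leave the non-compartmental cohort summaries as they are.

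The interim part is weaker. Both rifampin looks come at three infants per cohort, so using the same infants is a natural reading, though not a stated one. For clindamycin, the 8.7 h half-life comes from a study with no infant under 28 weeks' gestation. A longer half-life in infants of at most 26 weeks would bring the Cmax ratio nearer to 1.

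A reader might infer that the interim check would let an excessive dose through. The documents do not support that: no local doses are given, the illustrated shifts may be absent, and the safety reviews, halting rules and DMC operate regardless.

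**Conclusion.** The concern holds for the summaries of AUC0-24, AUCss and Cmax: in any cohort with mixed doses they describe no defined regimen, and their spread is not between-infant variability alone. On the assumptions above, the mean in rifampin cohort 4 could be 63–88% of the protocol-dose value with 10 mg/kg as the local dose. In cohort 1 at that dose nothing changes. The true size and direction are unknown. Local doses could also lie above the cohort dose: ticarcillin doses cited in 2.1 run from 50 to 100 mg/kg, either side of the protocol's 75 mg/kg.

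It would go too far to infer that the study's PK results as a whole are compromised. CL, Vss and t1/2 are unaffected under linear PK, the data are not harmed, and the doses needed for a correct summary are captured. The missing dose condition at the interim is secondary. It may not matter for rifampin, and for clindamycin cohort 1 the illustration moves Cmax but not AUC0-24. The change is worth making because these are declared primary outcomes and it is cheap.

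**What to change.** In 10.3:

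1. Within each age cohort, report AUC0-24, AUCss and Cmax by regimen received (protocol or local), with the number of infants in each. List individual values where cells are small.
2. Add dose-normalized AUC under a stated linear-PK assumption. Normalize Cmax only among infants with the same dosing interval.
3. Keep CL, Vss and t1/2 summarized by age cohort, combining regimens within each cohort. The age grouping must stay, because 2.1 reports that clearance changes with age.
4. State that the interim exposure check uses protocol-dose infants. Alternatively, use exposure predicted at the cohort's protocol dose, from individual CL for AUC (protocol daily dose / CL for AUC0-24) or from a fitted model for Cmax.

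The cost is a few sentences and slightly more output. Sections 7.1.1 and 7.1.5 already have doses and frequency recorded, so no blood draws or visits are added. The main drawback is small cells: 8 infants split evenly leave 4 per regimen. Restricting the interim check to protocol-dose infants could delay it. Prediction avoids the delay but relies on linear PK.

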#### **Interim PK analysis**

**Rifampin:** An interim PK analysis will be performed after enrollment of 3 participants in each cohort for rifampin. If the interim analysis suggests the PK data are sufficient to describe rifampin disposition in this patient population, enrollment will stop after 8 participants are enrolled in each cohort. If additional participants are required, the interim PK data will be used to determine the number of additional participants.

**Clindamycin:** An interim PK analysis will be performed after enrollment of 3 participants in cohort 1 for participants  $\leq 26$  weeks gestational age. If the interim analysis suggests the PK data are sufficient to describe clindamycin disposition in this patient population, enrollment will stop after 8 participants are enrolled in each cohort. If additional participants are required, the interim PK data will be used to determine the number of additional participants.

For both analyses, if the PK analysis suggests that drug exposure is below the maximum tolerated exposure in adults, no dosing modifications will be made.

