## 5 Study Population

### 5.1 Selection of the Study Population

**Rifampin:** 16 to 32 evaluable participants, at least 4 in each group

- Group 1: GA <32 weeks, PNA <14 days
- Group 2: GA <32 weeks, PNA ≥14 days–120 days
- Group 3: GA ≥32 weeks, PNA <14 days
- Group 4: GA ≥32 weeks, PNA ≥14 days–120 days

**Ticarcillin-clavulanate:** 16 to 32 evaluable participants, at least 4 in each group

- Group 1: GA <30 weeks, PNA <14 days
- Group 2: GA <30 weeks, PNA ≥14 days–45 days
- Group 3: GA <30 weeks, PNA >45 days–90 days

**Clindamycin:** 16 to 32 evaluable participants, at least 4 in each group

- Group 1: GA <30 weeks, PNA <14 days
- Group 2: GA <30 weeks, PNA ≥14 days–45 days
- Group 3: GA <30 weeks, PNA >45 days–120 days

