### 10.2 Sample Size Considerations

The sample size is based on the ability to observe a serious toxicity rate and to describe the PK. A sample size of 32 participants will provide adequate precision in the PK parameter estimates (i.e., CL) that will be dependent on the underlying variability of the parameter (see table below). For example, assuming an inter-individual coefficient of variance (CV%) of 40% in the population CL parameter estimate after weight-based allometric and maturation scaling, a sample size of 32 participants would provide a margin of error of  $\pm 14\%$  in the 95% confidence interval (CI) of the CL estimate.

The sample size is sufficient to describe the PK of these 3 antimicrobials.

PK Parameter CV%	95% CI Margin of Error
40%	$\pm 14\%$
50%	$\pm 17\%$
60%	$\pm 21\%$
80%	$\pm 28\%$

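### Whether PK data suffice, and how many infants to add, is decided from 12 infants for rifampin and 3 for clindamycin, although both PK branches enrol at least 8 per cohort anyway

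*Protocol*

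**What the plan says.** Protocol Section 10.3, Interim PK analysis, fixes the timing for two of the three drugs.

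- Rifampin: "An interim PK analysis will be performed after enrollment of 3 participants in each cohort for rifampin".
- Clindamycin: "An interim PK analysis will be performed after enrollment of 3 participants in cohort 1 for participants" of 26 weeks gestation or less. No infant from cohort 2 or 3 is required.
- For both drugs, if the PK data are judged sufficient, "enrollment will stop after 8 participants are enrolled in each cohort".
- Otherwise, if more infants are needed, "the interim PK data will be used to determine the number of additional participants".

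Ticarcillin-clavulanate has no interim PK analysis.

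Section 10.2 says that the precision of the PK estimates "will be dependent on the underlying variability of the parameter". It tabulates the margin of error for clearance at 32 participants for CVs from 40% to 80%, with a worked example "assuming an inter-individual coefficient of variance (CV%) of 40% in the population CL parameter estimate".

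Section 5.1 plans, for each drug, "16 to 32 evaluable participants, at least 4 in each group".

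**The concern.** The decision is taken at a point where it can save nothing. Neither PK branch ends below 8 per cohort, so infants 4 to 8 of each cohort are enrolled whatever the interim PK data show. Deciding at 3 leaves their data out of the one decision that needs them.

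The interim is also very small for judging variability. Rifampin has 12 infants in four cohorts that differ in gestational age, postnatal age and dose. Clindamycin has 3 infants from one gestational-age subgroup of one cohort, and their data decide sufficiency and added numbers for all three cohorts, which differ in postnatal age and dosing interval.

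An addition that is needed may therefore not be made, leaving clearance less precisely estimated than it should be. Or an addition may be made that better information would have shown to be unnecessary, which in this population means neonates enrolled without need.

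**Working it through.** **Inputs.** Interim sizes and the figure of 8 per cohort come from Section 10.3. The number of cohorts (four for rifampin, three for clindamycin) comes from Section 5.1. The 40% CV, the N of 32 and the margins come from Section 10.2. Two assumptions are added: that the between-infant CV of clearance is what the interim is used to judge, and that the normal approximation holds for its sampling error.

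**1. The protocol's own figures.** Margin = 1.96 × CV / √N. At N = 32:

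| CV | Computed margin | Section 10.2 |
|---|---|---|
| 40% | 13.86% | ±14% |
| 50% | 17.32% | ±17% |
| 60% | 20.79% | ±21% |
| 80% | 27.72% | ±28% |

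All four reproduce.

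**2. Enrolment if the data are judged sufficient.** Rifampin 4 × 8 = 32; clindamycin 3 × 8 = 24. If they are judged insufficient, more are added. On PK grounds these are floors.

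**3. Degrees of freedom for a within-cohort CV.**

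- Rifampin at the interim: 4 × (3 − 1) = 8. At 8 per cohort: 4 × (8 − 1) = 28.
- Clindamycin at the interim: 3 − 1 = 2. At 8 per cohort: 3 × (8 − 1) = 21.

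**4. 95% limits around an observed CV of 40%.** Limits = 40% × √(df / χ²), with χ² at its 97.5% and 2.5% points. The implied N for a ±14% margin is (1.96 × CV / 0.14)², rounded up.

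| Decision point | df | Multipliers | Limits on CV | Implied N for ±14% |
|---|---|---|---|---|
| Rifampin, 12 infants | 8 | 0.675 to 1.916 | 27–77% | 15–116 |
| Clindamycin, 3 infants | 2 | 0.521 to 6.285 | 21–251% | 9–1239 |
| Rifampin, 8 per cohort | 28 | 0.794 to 1.352 | 32–54% | 20–58 |
| Clindamycin, 8 per cohort | 21 | 0.769 to 1.429 | 31–57% | 19–65 |

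The interval from 3 infants is wider than the whole 40–80% range of the planning table. The N column shows how far the CV's uncertainty carries into a sample-size calculation; it does not forecast enrolment, because the floors in step 2 apply.

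**5. Chance of a misleading interim.** Suppose the true CV is 60%. The chance that the observed CV is 40% or less is P(χ² ≤ df × (40/60)²):

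- Rifampin: 10.5% at the interim, 0.5% at 8 per cohort.
- Clindamycin: 36% at the interim, 1.4% at 8 per cohort.

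In the other direction, suppose the true CV is 40%. The chance that the observed CV exceeds 60% is 10.5% with 2 df and 2.1% with 8 df.

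**6. What a wrong decision does.** A low reading leaves rifampin at 32, where a true CV of 60% gives ±21%. For clindamycin at 24 the same CV gives 1.96 × 60% / √24 = ±24%. A high reading adds infants; for rifampin any addition goes beyond 32.

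**The case against.** The strongest objection is that the CV-driven calculation is not in the protocol. Section 10.3 asks only whether the data suffice to describe the drug's disposition and does not say how an added number is derived. The criterion could stand in a statistical analysis plan that is not shown. This is right as far as it goes: the figures above are conditional on an assumption, and the missing formula is not a finding. But the protocol itself fixes the timing and size of the interim, and no formula repairs an estimate of variability with 2 to 8 degrees of freedom. Any other data-based criterion would rest on the same few infants.

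Three stronger readings are tempting and are not supported.

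- A reader might infer that a chance low CV closes the trial short of a ±14% target. Section 10.2 gives ±14% as an example, in the first row of a table that runs to ±28%, and rifampin cannot fall below the 32 infants on which that table rests.
- A reader might take the implied N of 15 to 116 as the range of final enrolment. Values below 32 cannot take effect for rifampin, and values above it collide with the 16–32 range in Section 5.1.
- A reader might describe the interim as 3 per cohort throughout. That is true only of rifampin.

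It can also be said that the early look serves other ends. It does: Section 10.3 also compares exposure with the adult maximum, and Section 8.1.4 sets safety reviews after the same numbers of infants. That is a reason to keep the look, not to size the trial from it.

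Finally, data from the POPS trial are to be co-modelled (Section 10.2, Population for Analysis) and would improve precision. The interim paragraphs do not say that they enter the interim decision.

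**Conclusion.** The point holds as a matter of timing. Section 10.3 ties sufficiency and any added number to 12 rifampin infants and 3 clindamycin infants, while both PK branches go on to at least 32 and 24. Waiting for data that will be collected anyway narrows the 95% limits on an observed CV of 40% from 27–77% to 32–54% for rifampin, and from 21–251% to 31–57% for clindamycin.

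The consequence is moderate. For rifampin, an addition may be wrongly withheld, leaving ±21% at a true CV of 60%, or wrongly triggered, taking enrolment past the stated maximum of 32 evaluable. Clindamycin is the weaker case, because 3 infants from one subgroup decide for three cohorts.

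The figures assume that the CV of clearance drives the decision, that variability can be pooled across a drug's cohorts, that the normal approximation holds, and that no safety review or halt (Sections 8.1.4 and 8.4) stops enrolment below 8 per cohort.

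**What to change.** Reword Section 10.3 as follows.

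- Leave the present early look, after 3 infants, unchanged for exposure and safety.
- Take the sufficiency decision, and set any additional number, when the cohorts of that drug reach 8.
- Base it on the residual variability of clearance pooled over all cohorts of the drug, with POPS data where available.
- Judge it against a stated precision margin chosen from the Section 10.2 table.
- Reconcile any addition with the 16–32 range in the synopsis and Section 5.1, since rifampin at 8 per cohort is already at 32.

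The cost is a text change and possibly a short enrolment pause at 8 per cohort while the model is run. No infant is added by waiting. The later estimate is better but still imprecise: for rifampin an observed CV of 40% would still imply an N of about 20 to 58 for ±14%, so the added number should be treated as approximate.

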## 11 PARTICIPANT CONFIDENTIALITY

Participants will be assigned unique code numbers and will not be identified by name. Participant confidentiality is held strictly in trust by the participating investigators, their staff, the sponsor(s), and their agents. This confidentiality extends to genetic and biological sample tests, in addition to the clinical information relating to participating participants.

The study protocol, documentation, data, and all other information generated will be held in strict confidence. No information concerning the study or the data will be released to any unauthorized third party without prior written approval of the sponsor.

The study monitor or other authorized representatives of the sponsor may inspect all documents and records required to be maintained by the investigator. This documentation includes, but is not limited to, medical records (office, clinic, or hospital) and pharmacy records for the participants in this study. Clinical study sites will permit access to such records.

The principal investigator will ensure that the use and disclosure of protected health information obtained during this research study complies with the Health Insurance Portability and Accountability Act (HIPAA) Privacy Rule. The rule provides U.S. federal protection for the privacy of protected health information by implementing standards to protect and guard against the misuse of individually identifiable health information of participants participating in clinical trials. “Authorization” is required from each research participant (i.e., specific permission granted by an individual to a covered entity for the use or disclosure of an individual’s protected health information). A valid authorization must meet the implementation specifications under the HIPAA Privacy Rule. Authorization will be combined in the informed consent document (approved by the IRB).

